DNA Collection and Extraction. DNA will be extracted from blood samples collected by a member of the study staff who is also a certified phlebotomist, labeled by coded identifiers, and sent to [name] laboratory at MGH for genotyping. If a patient is interested in providing a genetics sample but is unwilling to have their blood drawn, they will have the option to provide a saliva sample. Laboratory personnel will not have access to personal identifiers. [name] laboratory has extensive experience with the collection, extraction and genotyping of DNA. The process of DNA collection through blood and saliva samples is highly acceptable to participants and, in our hands, each sample provides approximately 60 ug of genomic DNA. Given that each genotyping assay requires only 2.5 – 5 ng of DNA, this yield will be more than adequate. After DNA extraction, sample yield is determined by picogreen analysis.

Genotyping Methods: Genotyping will be performed in [name] lab at the MGH Center for Human Genetic Research. Single nucleotide polymorphism (SNP) genotyping will be performed using the Sequenom MassArray system (Tang et al., 1999; Smoller et al., 2003). Genotyping will be performed in multiplex reactions in 384-well plates. For each assay, four duplicate samples and 4 blank samples will be included. SNPs will be used for association analyses only if they meet the following quality control criteria: 1) >90% of attempted genotypes for any SNP are successful, 2) alleles are in Hardy Weinberg equilibrium, and 3) agreement between all

duplicates and no more than 1 of 4 blanks with genotypes. Genotyping of the functional promoter variant in the *GRIN2A* gene (Itokawa et al., 2003) will be performed using the Applied Biosystems 3730 DNA Analyzer and standard protocols. GeneMapper v3.5 is used to analyze the raw results from the ABI3730, however, a genotype is not considered final until two laboratory personnel have independently checked (and corrected) the GeneMapper results and both individuals are in agreement.

Given the small number of genetic samples, we will add BDD DNA samples collected by the PI for a separate BDD treatment study of Lexapro discontinuation as well as BDD DNA samples collected by project collaborator [name] at Brown University as part of a longitudinal BDD study. Both studies obtained consent for participants to collect DNA, to store this DNA at MGH, and to conduct genetic association studies for BDD. Only subjects who specifically consented for the genetic portion of the study had blood drawn and DNA extracted; therefore, only subjects who consented for the optional genetic study will be used for the current genotyping study. All DNA tubes/samples are fully de-identified. For the samples collected at Brown, no MGH investigators have any access to subject identifiers.

In order to conduct a BDD case-control genetic association study, we have obtained ancestry and gender-matched control DNAs from the Genome Superstruct Project (GSP), (Massachusetts General Hospital, Boston; PI: [name], [name], [name]). All of these control samples were consented for genotyping in targeted and whole-genome association studies as well as for data sharing. No control subjects who did not consent to future sharing will be used in this study. Of note, we need to conduct direct genotyping of the BDD candidate genes to control for likely experimental confounds if the BDD case DNAs were genotyped and compared to control data generated on a different platform at a different site. The DNAs all exist in the MGH PNGU Core Lab, and are fully de-identified; thus, BDD study investigators have no way of knowing to whom the samples belong.

Privacy and Confidentiality

All information gathered will be kept strictly confidential. Participants will be assigned a code number, and the participants' names will not appear on any questionnaires or therapy protocols. Moreover, the data will be stored in locked file cabinets located in locked offices. Only the study personnel will have access to the data.

Participants may also choose to provide consent for the use of their samples in related research. We have included in the consent form a description of what information will be shared with any outside investigators.

6. Biostatistical Analysis

Please note: The blind may be broken after every ten subjects to conduct preliminary analyses to assess for the efficacy of D-cycloserine.

Primary analyses: Our primary hypothesis is that ERP in combination with DCS is more effective than ERP in combination with a placebo. To measure this, the BDD-YBOCS will be the primary outcome measure. The main analyses will compare the two patient groups at mid-treatment and post-treatment using analysis of variance (ANOVA) and analysis of covariance (ANCOVA, controlling for BDD-YBOCS-pretreatment scores). To further determine the clinical significance of these findings, we will use the Jacobson and Truax (1991) formula to calculate the percentage of patients who fulfill the criteria for reliable and clinically significant change in each treatment condition at mid-treatment and post-treatment. Fisher's exact test for differences in frequencies of responders between the two patient groups will be performed. We will further compare the two groups at the 1- and 6-month follow-up assessments.

Power analysis: A power analysis with a sample size of 25 per group and $p < .05$ reveals that this study will convey 80% power to detect a group difference in post-treatment BDD-YBOCS scores of $d = 0.78$, which is a large effect size. Moreover, we will estimate between-group effect sizes of this pilot study to be used in designing future studies.

Secondary analyses: We hypothesize that patients who receive DCS augmentation will have greater improvement on the CGI-I, BDI, BDD-SS, and Disability Inventory at mid-treatment, post-treatment and 1- and 6-month follow-up assessments than patients who receive the placebo. ANCOVAs (controlling for pretreatment scores) and multivariate ANCOVAs (MANCOVAs) will be used for these analyses as described above, and effect sizes will be computed. Furthermore, the Cognitive and Behavioral Change Measures will be used to identify in more detail within which session, or between which sessions, any changes occurred.

Predictors of outcome: We also wish to evaluate whether ERP in combination with DCS is particularly effective or ineffective for different symptoms (as measured by the BDD Symptom Scale), attitudes (i.e., patient's judgments about the credibility of the treatment, as measured by the Expectancy Rating), or comorbid problems (e.g., depression). These factors will be included in regression analyses. We also intend to explore the relationship between minority status and treatment outcome; however, power will be limited given the small sample size.

Mechanisms of improvement: We are also interested in potential mechanisms of change during treatment. These can be tested with multiple regression procedures via hierarchical regression models. Treatment group (DCS vs. placebo) will be the independent variable, changes in BDD symptom severity (BDD-YBOCS) the dependent variable, and, for example,

changes in beliefs as measured by the Schema Questionnaire will be the mediator. We will follow the procedures for establishing statistical mediation outlined by Baron and Kenney (1986), using residual gain scores as the measure of change in both the dependent variable and the mediator (Cohen, 1983). These residual scores will give a reliable estimate of changes in symptom severity and beliefs independent of differences in baseline severity. We will interpret our results with caution because the absence of statistical significance may reflect the somewhat limited power with only 50 patients.

Genetic Analyses: We will use quantitative trait association analytic methods to examine whether alleles and/or haplotypes of the loci selected for analyses are associated with outcome of ERP with or without DCS. Analyses will be conducted in two stages. The initial analyses will examine whether any of the genetic variants are associated with ERP outcome indexed by change in BDD-YBOCS score from baseline (at end of treatment and at 1-month and 6 month follow-up). The analyses will include a main effect analysis of each genetic variant as well as a gene x treatment interaction analysis, to examine whether allelic effects on outcome differ by treatment condition (DCS vs. placebo). If evidence of interaction is detected, we will also examine allelic effects within treatment group. For example, we expect that genes involved in NMDA receptor function (e.g. the *GRIN1* gene whose product includes the glycine (DCS) binding domain) may mediate response to DCS.

In the second stage, genetic predictors demonstrating univariate association will be entered into a multivariable linear regression model along with other predictors of treatment response in an effort to build a model that parsimoniously explains the greatest proportion of variance in response to ERP (with and without DCS). For genes in which more than one polymorphism shows evidence of association, we will select the SNP with the minimum p value to enter into the multivariable model.

Univariate single marker and haplotype-based analyses will be conducted using WHAP (Curran et al., 2005; <http://www.broad.mit.edu/~shaun/whap/>). Using an approach similar to those of Schaid et al. (2002) and Zaykin et al. (2002), WHAP is based on a two-stage method. The primary test is a regression-based analysis of association between marker (or haplotype) and trait, with one regression coefficient per marker (or haplotype). The independent secondary test analyses the relationship between marker (or haplotype) similarity and regression coefficient similarity. Evidence from the primary and secondary stages can be combined to provide a more powerful test of association, by combining log-transformed P values. The method is based on a mixture of regression models which accounts for the potential ambiguity in individuals' statistically-inferred haplotypes. For H haplotypes, a single omnibus test is performed to test jointly for any difference in haplotype effect, which is an H

– 1 single-degree-of-freedom test. The independent secondary test assesses whether pairs of more similar haplotypes show more similar effects. A multivariate weighted least squares regression of haplotype effect similarity on haplotype genetic similarity is used and empirical significance levels are determined by permutation testing. We will define haplotype blocks using the conservative definition of Gabriel et al. (2002) as implemented in Haploview (Barrett et al., 2004).

Evaluation of Population Structure. It has been well recognized that ethnic admixture or population stratification may confound case-control genetic association studies, although the importance of this phenomenon has been debated (Freedman et al., 2004; Wacholder et al., 2002). Nevertheless, we will evaluate the possibility of confounding due to population stratification, by typing a panel of 100 informative unlinked (null) SNPs. The main approach used will be that described by Purcell and Sham (2004), which implements a method very similar to that of Pritchard et al. (2001) and Satten et al. (2001). All these approaches look for Hardy-Weinberg disequilibrium and LD between unlinked markers, and probabilistically break down the sample to a number of subgroups, within which Hardy-Weinberg equilibrium and linkage equilibrium hold (as one would expect in a homogeneous population). We will evaluate population structure by performing analyses using the L-POP program (Purcell et al., 2004). Because the sample is expected to be primarily Caucasian, if more than one subgroup is detected, we expect that only one subgroup will have sufficient power for analysis. Thus our analyses would focus on the largest subgroup.

7. Risks and Discomforts

Patients may feel uncomfortable due to the sensitive nature of the questions they may be asked.

Side effects. The potential side effects associated with the administration of DCS include drowsiness, headache, prolonged or momentary dizziness, seizures, confusion, hallucinations, weakness, coma, rash, vitamin B₁₂ deficiency and/or folate deficiency (both of which may cause weakness and anemia (low blood counts)), liver enzymes increases (which could cause weakness or bleeding), and shaking. However, these side effects are most commonly related with doses greater than 500mg/day, which is five times what is administered in this study. The use of DCS at doses of 100 mg (as in this study) does not appear to be associated with significant emergent adverse effects. Indeed, in our recent trial examining the efficacy of DCS augmentation of behavior therapy for individuals with OCD no subjects reported any side effects as a result of the study medication.

Interactions.

(1) Intake of alcohol at the same day may increase the possibility and risk of epileptic episodes. Thus, we will exclude patients with current alcohol dependence. Furthermore, we will instruct the patients not to consume any alcohol 12 hours prior to and 24 hours after receiving the study medication. To ensure that patients have not consumed alcohol prior to taking the study medication we will administer a saliva test to measure BAC levels immediately before dispensing the medication.

(2) Intake of Isoniazid at the same day may result in increased CNS side effects. Thus, we will exclude patients who currently take Isoniazid.

Optional Genetics Component

There is a risk associated with the sensitivity of the genetic information. The results of genetic analyses will be kept confidential and will not be returned to participants in this study. Consequently, the potential risks of subjects learning sensitive genetic information or of discrimination related to participation in a genetic study should be avoided. There is a theoretical risk of discrimination by employers or insurers should subjects' enrollment into or the results of the study unintentionally become known despite procedures in place to maintain confidentiality. The following steps will be taken to protect the confidentiality and privacy of the genetic data:

- a. No genetic research data will be entered into the medical record.
- b. The results of the genetic analyses will not be shared with participants or their family members.
- c. Only coded identifiers, rather than personal identifiers, will be used in any analytic datasets. The genetic laboratory will not have access to personal identifiers.

To protect confidentiality, information about subjects will be stored in research files identified only by code. The code key connecting IDs to identifying information will be kept in a separate secure location at the research site at which a participant is enrolled. Data in databases is similarly identified only by coded ID number and is password-protected.

Minimizing of Risks and Safety Reporting. Subjects will be monitored in an ongoing manner for side effects or any adverse reactions to the study medication. The study physicians, Drs. [name] and [name], will review all reports of adverse events and forward them to the IRB. Patients may also contact them at any time to discuss their medication, side effects, or adverse reactions.

Adverse event reporting: In case of an adverse event and in accordance with Partners Human Research Committee Adverse Event Reporting Guidelines, we will complete the appropriate adverse event form and forward it to the IRB within the required time frame for reporting.

8. Potential Benefits

Patients may benefit by experiencing some relief from their BDD symptoms. Our research will help us better understand what treatments are beneficial in this disorder.

9. Monitoring and Quality Assurance

[name] and [name] will be responsible for ensuring that all study procedures are conducted according to the IRB-approved protocol and reviewing the accuracy and completeness of source documents. [name] and [name] will meet with [name] regularly to discuss the study procedures and progress. Drs. [name] and [name] will be responsible for ensuring that the study treatment is delivered appropriately.

Subjects will be monitored in an ongoing manner for side effects or any adverse reactions to the study medication. The study physicians will review all reports of adverse events and forward them to the IRB according to Partners guidelines. Participants may also contact the study physicians at any time to discuss their medication, side effects, or adverse reactions. The PI, in collaboration with the study physicians will ultimately be responsible for determining whether the research should be altered or stopped.

Participants will be withdrawn from the study if their clinical condition deteriorates substantially. Deterioration will be defined by a rating of 6 (much worse) or 7 (very much worse) on the CGI-I. Participants may also be withdrawn if in the judgment of the PI or therapist remaining in the study poses a substantial risk to the participant or a higher level of care is needed.

In case of an adverse event and in accordance with Partners Human Research Committee Adverse Event Reporting Guidelines, we will complete the appropriate adverse event form and forward it to the IRB within the required time frame for reporting.

10. References

Alliez, J., & Robin, M. (1969). Aspects psycho-pathologiques de la defiguration leur relation avec dysmorphophobie [Psychopathologic aspects of disfiguration; their relation to dysmorphophobia]. *Ann Med Psychol*, 2, 479-94.

- American Psychiatric Association (1994). Diagnostic and statistical manual of mental disorders, 4th edition. Washington, DC, American Psychiatric Association Press.

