We hypothesize that genes implicated in fear extinction will provide general prediction of the success of exposure treatment, and that the degree of additional benefit associated with DCS will be influenced by NMDA-related glutamatergic loci.

3. Subject Selection

Inclusion criteria are a diagnosis of BDD by DSM-IV standards and a BDD Yale-Brown Obsessive Compulsive Scale score greater than or equal to 24 in people 18 years of age or older. Subjects must be able to give informed consent, and females of childbearing potential must have a negative urinary beta-HCG test. Pregnant or breastfeeding women, people taking medications that may interfere with DCS, and people with a history of seizure disorder or other serious medical illnesses such as cardiovascular, hepatic, renal, respiratory, endocrine, neurological or hematological disease are excluded from this study. Other criteria for exclusion are comorbid

psychiatric diagnoses (alcohol dependence, bipolar disorder, psychosis, borderline personality disorder, organic mental disorder, or developmental disorder). Also excluded are patients taking medications that may lower the seizure threshold, including clozapine, pethidine, and the following antibiotics in high dosages: penicillins, cephalosporins, amphotericin, and imipenem. Those deemed to pose a serious suicidal or homicidal threat will be excluded. If patients have any other comorbid disorder, the BDD symptoms must be the primary concern. Furthermore, current psychotherapy and failure to benefit from ten or more sessions of previous CBT treatment are a rule-out. Moreover, if a patient is taking a psychotropic medication, he or she must be at a stable dose prior to enrolling in the study.

Participants will be withdrawn from the study if their clinical condition deteriorates substantially, as defined by a rating of 6 (much worse) or 7 (very much worse) on the Clinical Global Impressions-Improvement (CGI-I) scale. Participants may also be withdrawn if, in the judgment of the PI or therapist, remaining in the study poses a substantial risk to the participant, or if a higher level of care is needed.

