At the initial visit, we will first obtain informed consent from the participant. We will also have participants sign their initials and date if they consent to sharing their de-identified data with other researchers in our group or across studies for research purposes only. This procedure will save subjects time if they participate in more than one study at our clinic because it will eliminate repeating assessments shared between studies. The participant will then undergo a structured clinical interview and fill out several questionnaires assessing BDD symptoms, anxiety, and depression. If the participant is eligible for participation based on this evaluation, the study physician will then meet with him or her to conduct the medical evaluation (more detail below). If the participant remains eligible for the study after the medical evaluation then he or she will be randomized to receive either the D-cycloserine or placebo. The MGH research pharmacy will create and maintain the coded randomization schedule for this double-blind design and prepare and dispense the study medication (DCS or placebo) to study staff. None of the investigators will be privy to the code, except for the study physician in case of an emergency. Participants who choose to participate in the optional genetics component of the study will also have their blood drawn at this visit. In all, the initial visit will last approximately 3-4 hours. After randomization, the participant will come to the clinic for a psychoeducation/treatment planning session approximately one week later (see below for more detail). If we are unable to schedule the treatment planning session within 21 days of the screening visit, participants will be asked to complete a modified screening session directly prior to the treatment planning session. This visit will take approximately 30 minutes. This visit will last approximately 1.5 to 2 hours. The participant will not take the study medication/placebo prior to this visit. After this treatment planning session the participant will be scheduled for 10 once weekly behavior therapy sessions over a 10 week period. The first two therapy sessions will involve primarily cognitive interventions and so the study medication will not be administered prior to these sessions. The participant will be asked to come to the clinic one hour before sessions 3-10 to take the study medication/placebo in the presence of the therapist. Study medication will be kept at the clinic for the duration of the study. In addition to the therapy visits, comprehensive assessments of BDD symptoms, mood state and cognitions to assess the outcome of therapy will be given at midtreatment (after session #5), post treatment and at 1- and 6- month follow-ups. These assessments will take approximately 1 hour. BDD symptoms, CGI-I score, and depressive symptoms will be assessed via self-report questionnaires at every treatment session. These questionnaires

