
will take approximately 5 minutes to complete. A detailed assessment schedule is submitted for review.

Psychological Assessments

Comprehensive assessments of BDD symptoms, mood state and cognitions to assess the outcome of therapy will be given at pretreatment, midtreatment, post treatment and at 1- and 6- month follow-up. BDD symptoms, CGI-I score, and depressive symptoms will be assessed every treatment session.

The following instruments will be used and are submitted for review:

(1) Demographic information sheet. This sheet assesses general information such as age, years of education, etc.

(2) Structured Clinical Interview for DSM-IV (SCID; First, Spitzer, Gibbon et al., 1995). This instrument will be used to determine the Axis I psychiatric diagnosis(es).

(3) Structured Clinical Interview for DSM-IV Axis II Personality Disorders (SCID-II; First et al., 1997). Patients will complete the SCID-II self-report questionnaire; for any personality disorder for which the patient's report approaches criterion (number of criteria required minus 1), the rater will administer all interview questions for that personality disorder.

(4) Yale Brown Obsessive Compulsive Scale modified for BDD (BDD-YBOCS). This reliable and valid 12-item semi-structured clinician-administered scale, which was adapted from the Y-BOCS (Goodman et al., 1989), rates current severity of BDD symptoms (Phillips et al., 1997). It will be the study's primary outcome measure. The BDD-YBOCS has excellent interrater and test-retest reliability (ICC for total score=.99 and .88, respectively), internal consistency (Cronbach's alpha=.80), convergent validity ($r=.55$ with the CGI), and sensitivity to change with treatment (Phillips et al., 1997).

(5) BDD-Symptom Scale (BDD-SS) The PI developed the BDD-SS to rate the severity of specific BDD symptoms.

(6) Clinical Global Impression Scale (CGI) This global rating scale, which ranges from 1 (very much improved) to 7 (very much worse) on levels of improvement (CGI-I) and from 1 (normal, not at all ill) to 7 (extremely ill) on severity (CGI-S), is commonly used in pharmacotherapy trials (Guy, 1976). The CGI will be a secondary outcome measure and will also be used to determine clinical deterioration of BDD.

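### Withdrawal from the study at a CGI-I of 6 or 7 leaves poor outcomes with no stated later BDD-YBOCS, analysis set or place in the responder test; the likely bias is small and the remedy cheap

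*Combined protocol and SAP*

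**What the plan says.** The rule stands in section 3 (Subject Selection): "Participants will be withdrawn from the study if their clinical condition deteriorates substantially, as defined by a rating of 6 (much worse) or 7". Section 9 (Monitoring and Quality Assurance) repeats it: "Deterioration will be defined by a rating of 6 (much worse) or 7 (very much worse) on the CGI-I". Both places speak of leaving the study, not only of stopping study medication, and neither adds any follow-up. Section 3 also has a discretionary route: "Participants may also be withdrawn if, in the judgment of the PI or therapist, remaining in the study poses a substantial risk".

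The trigger is itself an outcome. Section 5 (Psychological Assessments) says "The CGI will be a secondary outcome measure and will also be used to determine clinical deterioration of BDD". The primary measure, the BDD-YBOCS, is described there as "This reliable and valid 12-item semi-structured clinician-administered scale".

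On timing, section 5 (Overview) says that the comprehensive assessments "to assess the outcome of therapy will be given at midtreatment (after session #5), post treatment and at 1- and 6- month follow-ups". It adds: "BDD symptoms, CGI-I score, and depressive symptoms will be assessed via self-report questionnaires at every treatment session". It also mentions a detailed assessment schedule, which is not in the supplied text.

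Section 6 (Primary analyses) compares the arms on the BDD-YBOCS at mid-treatment and at post-treatment by ANOVA and by ANCOVA adjusted for the pretreatment score. It then compares the proportion of patients in each condition who meet the Jacobson and Truax criterion, using Fisher's exact test, and compares the arms again at 1 and 6 months. It names no analysis set, no method for missing scores and no rule for classing withdrawn participants.

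**The concern.** A mandatory rule tied to an outcome removes people because they are doing badly. An ANOVA or ANCOVA at a single visit cannot use a person with no score at that visit, so the silence in section 6 leads to a comparison among those who remain. If more placebo participants deteriorate, the benefit of DCS is understated. If more DCS participants deteriorate, harm is understated and the DCS responder percentage rises.

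The responder denominator is open as well. Whether withdrawn people are counted can change a percentage and, in a borderline table, the p-value. Section 6 allows the blind to be broken after every ten subjects, so an unwritten choice could be made with arm-level results in view. It also says that effect sizes from this pilot will be used to design later studies, so the estimate matters beyond its p-value.

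**Working it through.** **1. The plan's own figure.** Section 6 gives 80% power for d = 0.78 with 25 per group at p < .05. By the normal approximation, power = Φ(d·√(n/2) − 1.96) = Φ(0.78·√12.5 − 1.96) = Φ(0.798) = 78.7%, which reproduces the statement to within 2 points (noncentral t: 77.1%). It needs a post-treatment score from all 50. Losing 1, 3 or 5 per arm gives 77.1%, 73.5% or 69.4% by the same formula. Section 2 raises enrolment to 80 for screening failures only.

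**2. Which visits lose a score.** The text does not say which CGI-I rating is the trigger.
- Per-session rating: withdrawal can come before the mid-treatment or post-treatment assessment, so a score can be lost at either, and at 1 and 6 months.
- Comprehensive-assessment rating only: a BDD-YBOCS would be expected at that same assessment and only later visits are lost. Mid-treatment is unaffected; a trigger at mid-treatment costs post-treatment; any trigger costs the remaining follow-up.

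Under either reading the 1- and 6-month comparisons lose these people. Withdrawals at sessions 1-2 cannot be caused by the drug: "The first two therapy sessions will involve primarily cognitive interventions and so the study medication will not be administered prior to these sessions".

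**3. Size of the bias in d.** The documents give no deterioration rate, so 2-4% on placebo is an assumption.
- Expected number: 25 × 0.02 = 0.5 to 25 × 0.04 = 1.
- Chance of at least one among 25: 1 − 0.98^25 = 0.40; 1 − 0.96^25 = 0.64.
- Standard error of d: √(2/25 + 0.78²/100) = 0.293.

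A weekly simulation with 600,000 per arm used these assumptions:
- BDD-YBOCS = 0.5 × baseline + autoregressive residual (autocorrelation 0.8 or 0.95), total SD 1.
- Latent CGI-I correlated 0.55 or 0.9 with that residual; CGI-I noise autocorrelation 0, 0.8 or 0.95.
- Drug effect zero through session 2, then linear to d at session 10.
- Withdrawal at the first crossing of a cutoff set to give the placebo rate.

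ANCOVA among those with a score then estimates:
- True 0.78, per-session trigger: 0.763-0.773 at 2%; 0.750-0.768 at 4%.
- Mid-treatment, true 0.78 × 3/8 = 0.2925: 0.283-0.291.
- True 0.78, comprehensive-assessment trigger (noise autocorrelation 0.8): 0.764-0.778.
- True −0.30, that is DCS worse, per-session trigger (noise autocorrelation 0.8): −0.274 to −0.296.
- True 0 (same setting): within 0.001 of zero.

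The largest shift is 0.78 − 0.750 = 0.03, about a tenth of the standard error.

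**4. The responder test** (two-sided Fisher, illustrative counts, not a forecast).
- 15/25 (60%) v 8/25 (32%): p = 0.088.
- One withdrawn DCS non-responder dropped, 15/24 v 8/25: p = 0.047.
- Three withdrawn placebo non-responders dropped, 15/25 v 8/22: p = 0.147. Three of 25 is 12%, well above the assumed range.

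How often this matters: of the 650 tables of 25 v 25 with at least one DCS non-responder to drop (26 × 25), 20 with DCS ahead move from p ≥ .05 to p < .05 when one is dropped. With withdrawal of 1.3-2.6% on DCS and 2-4% on placebo, the two denominators disagree on significance in about 0.6-1.2% of trials when response is equal (40% or 50%), and in about 2.7-4.3% when it is 60% v 32%.

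**The case against.** The plan nowhere says that withdrawn participants are excluded; that is inferred from silence. The responder percentage refers to patients in each treatment condition, which can fairly be read as everyone in the arm, with withdrawn people as non-responders. The assessment schedule that was not supplied may contain a termination visit. By the figures above the bias is negligible, and the Fisher example is a chosen borderline table: any small trial has tables that turn on one person. What remains is a general gap that applies to all dropout.

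Much of this stands. A termination visit would answer the question of a withdrawal score, but would supply neither an analysis set nor a responder rule. The favourable reading of the percentage is possible, but the text does not settle it. The gap is more than missing detail, because a stated and mandatory rule ends participation for people selected by a poor outcome.

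The simulation also has a limit: it gives withdrawn DCS participants the full drug effect at session 10 although they have stopped. If their effect is frozen at withdrawal, the all-randomised effect is 0.760-0.775, and the ANCOVA among those with scores differs from it by about −0.017 to +0.005. That makes the bias smaller and its sign uncertain.

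A reader might infer a serious distortion. Fixing the loss at the worst 3 of 25 on DCS and the worst 1 of 25 on placebo, with no true effect, shifts the difference by about 0.13-0.14 SD and gives about 10% false positives. The documents do not support that reading: they give no withdrawal rate and no reason for such an imbalance, and it assumes that exactly the worst scores are always the ones removed. With one rule applied alike in both arms and no true effect, the bias is about zero.

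**Conclusion.** The point holds in a limited form. As written, participants withdrawn for deterioration have no described BDD-YBOCS afterwards, so the ANOVA/ANCOVA would leave out outcome-related poor results: certainly at 1 and 6 months, and at post-treatment or mid-treatment depending on which CGI-I rating triggers withdrawal. Discretionary withdrawals share the gap.

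At an assumed 2-4% placebo withdrawal the bias in d is about 0.03 or less, and near zero under the null. The practical weight lies in the unstated analysis set and responder denominator, which can decide a borderline test, and in the pilot's effect sizes feeding later designs. The conclusion rests on the supplied text alone, on assumed rates, and on the unseen schedule having no termination visit. It is a cheap improvement of minor to moderate weight. It does not show that the planned result would be materially biased or would favour DCS.

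**What to change.** Leave the clinical criterion and all treatment decisions as written. First check the assessment schedule for a termination visit, and have the sponsor state which CGI-I rating the rule refers to. Then add:

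1. Withdrawal does not by itself end outcome assessment. Obtain a BDD-YBOCS at withdrawal and invite willing participants to the assessments already scheduled, except where the investigator judges further contact to be a risk.
2. Analyse all randomised participants in their assigned arm with a baseline-adjusted repeated-measures model using every available BDD-YBOCS. Do not relabel a withdrawal score as a later visit in the main analysis, least of all one taken at sessions 1-2 before any study drug. Carry it forward only as a sensitivity analysis. State that the effect estimated includes post-withdrawal scores.
3. Use all randomised as the Fisher denominator. Anyone without a qualifying score at that visit is a non-responder.
4. Report number, reason and timing of withdrawals by arm, with sessions 1-2 shown separately.

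The cost is a few sentences of protocol and analysis text, one extra BDD-YBOCS per withdrawal, and some additional completions of existing visits. The downsides are a small burden on people who have stopped, and later scores that may reflect other care. For those who decline all further contact, the model still relies on the scores already recorded, so the fix reduces the problem without removing it.
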